5.7 Liver biopsy

Liver biopsies will be performed 52 weeks after enrollment (window: 44-64 weeks) by the NASH CRN principal investigator or designee. Liver biopsies will generally be obtained from the right lobe of the liver using a 16G or larger biopsy instrument (if the initial biopsy was obtained from the left lobe, then the 52 week biopsy must be obtained from the left lobe). Biopsies should be at least 1.5 cm in length.

5.8 Specimen repositories

Specimens will be collected and stored in the NIDDK central repositories for use as approved by the Steering Committee of the NASH CRN (see Appendix 10.3 for blood collection schedule). Specimens include serum, plasma, DNA, and liver tissue. The blood collected during screening, and at the 12, 24, 36, 52, and 76 week follow-up visits will be separated into plasma and serum, and divided into 0.5 mL aliquots. Aliquots will be kept in a storage facility at -70 degrees C until they are

shipped to the NIDDK Biosample Repository on dry ice. If the patient provided additional consent, blood will be collected during screening and shipped to the NIDDK Genetics Repository for extraction of DNA and banking. When possible, a portion of the liver biopsy specimen will also be collected in RNA*later*[®] and refrigerated at 4° C overnight to allow thorough penetration of the liver tissue and then transfer to -70° C freezer for storage.at -70 degrees C until shipping to the NIDDK Biosample Repository on dry ice.

5.9 Adherence and retention

Two important goals of this protocol are to optimize adherence to the pharmacological regimen and to maximize the retention of participants in the study. Assessment of adherence to the assigned study drug will provide clinic staff a means to identify participants having problems with adherence. Adherence will be assessed by:

- Counts of capsules in the patient's returned study drug bottles
- Conducting a brief, structured interview, in which the study coordinator will assist the patients to identify problems in taking the study drug and to estimate adherence to the prescribed medicine since their previous visit.

These assessments will guide the consideration of strategies to improve adherence. Resources will be provided to remove barriers to participation such as child or elder care, transportation, and parking expenses. These resources can be provided as cash, transportation vouchers, or parking passes. An honorarium may be paid to participants in recognition of their time and effort when scheduled visits and procedures are completed successfully. Certificates of appreciation may be given at enrollment and at conclusion of the CyNCh trial as an incentive.

5.10 Management of concomitant conditions

Hypertension, hyperlipidemia, and diabetes will be managed in conjunction with the patient's primary care physician according to the protocols described in the Standard of Care document prepared by the Pediatric Standard of Care Committee of NASH CRN.

Pregnancy will be managed according to the guidelines shown in section 6.10. In the event of major dermatological reactions such as generalized urticaria, bullous rashes, exfoliative dermatitis, or Stevens-Johnson Syndrome, study drug will be discontinued immediately and not restarted. For local skin reactions, study drug may be discontinued if the skin reactions are potentially drug related. If the rashes clear, the study drug may be restarted.

If local skin reactions recur with restarting the study drug, study drug should be discontinued. In cases where the study medication has been discontinued, the study drug will be unmasked and the participant, investigator, and the primary care provider will be notified in order to prevent future exposures.

6. Safety monitoring

6.1 Historical safety issues in children with nephropathic cystinosis taking immediate release cysteamine bitartrate (Cystagon[®]) capsules

Cystinosis is a rare genetic disorder that causes an accumulation of the amino acid cystine within cells which causes a myriad of problems including damage to the skin, eyes, kidneys, liver, endocrine system, hematologic system, and the central nervous system. The treatment for cystinosis has been immediate release cysteamine 4 times per day since Cystagon[®] was approved by the FDA in 1994. The dosing of Cystagon[®] for children with nephropathic cystinosis is between 1.30 grams/m²/day and 1.95 grams/ m^2 /day. At this dose, immediate release cysteamine is known to have common gastrointestinal side effects including vomiting, anorexia, and diarrhea. In clinical trials of Cystagon[®], withdrawals due to intolerance, vomiting associated with medication, anorexia, lethargy, and fever appeared dose related, occurring more frequently in children receiving 1.95 grams/ m^2/day as compared to 1.30 grams/m²/day. Immediate release cysteamine is also associated with side effects that may be attributable to the underlying disease, cystinosis, rather than the medication itself. These include symptoms such as reversible leucopenia, abnormal liver function studies, skin lesions, headache, tinnitus, diplopia, blurry vision, loss of vision, pain behind the eye or pain with eye movement. Moreover, in children with cystinosis treated with doses > 1.95 grams/ m²/day there were additional side effects. Children treated with high doses of cysteamine may develop skin lesions. These include skin striae (which are like stretch marks), bone injuries (such as fractures), bone deformities, and joint problems. Benign intracranial hypertension (or pseudotumor cerebri) with papilledema; skin lesions, molluscoid pseudo tumors, skin striae, skin fragility; joint hyperextension, leg pain, genu valgum, osteopenia, compression fracture and scoliosis have been reported in patients taking immediate-release cysteamine.

Although these historical data are important background information, it is important to note:

- 1. The CyNCh trial will NOT enroll any children with nephropathic cystinosis
- 2. The CyNCh trial will NOT utilize immediate-release cysteamine
- 3. The CyNCh trial will use a MUCH lower dose of cysteamine than even the lowest dose ever used for nephropathic cystinosis

6.2 Safety issues in children with NAFLD taking delayed release cysteamine bitartrate (RP103) capsules

For the reasons above, efforts over the past decade were focused on improving the side effect profile of cysteamine therapy by changing the location and rate of drug release. To this end an enteric coated cysteamine (EC-cysteamine) capsule was developed⁶⁰. In patients with cystinosis, at the high doses required, EC-cysteamine was shown to have better GI tolerability than immediate release cysteamine. EC-cysteamine was then used in a pilot study as a therapy for children with NAFLD. At the high dose of 1000 mg orally twice a day, abdominal pain, nausea, and/or vomiting was noted in 5 of 13 children (38%)⁶⁰. Notably, however, a clinical response to EC-cysteamine was seen at the much lower dose of 300 mg taken orally twice a day. At this dose, which was selected for patients weighing ≤ 65 kg in the CyNCh Trial, gastrointestinal tolerance was satisfactory. Nausea and/or abdominal pain were noted in only 2 of 13 children (15%). Moreover, these symptoms resolved completely in less than 2 weeks with tolerance of this dose thereafter in all children. In order to take advantage of the improved pharmacokinetics resulting from enteric-coating, Raptor Therapeutics, Inc. has developed delayed-release capsules (RP103), with cysteamine bitartrate formulated in microspheronized core beads that are subsequently enteric-coated. The enteric-coated core beads are then encapsulated in gelatin capsules (Raptor Therapeutics Inc. Cysteamine Bitartrate Delayedrelease 75 mg capsules, Investigator's Brochure, 1st Edition-January 13, 2012). This new

formulation, RP103 75 mg capsules is being used in the CyNCh Trial. RP103 was approved by the FDA in April 2013 for the treatment of nephropathic cystinosis (Raptor Therapeutics Inc., PROCYSBI (cysteamine bitartrate delayed release capsules, Investigator's Brochure, April 2013). The dosing in CyNCh will be based upon weight not body surface area as done for cystinosis, but the average dose of RP103 will be $0.470 \text{ grams/m}^2/\text{day}$, which is much lower than the dose of cysteamine used in the treatment of children with cystinosis ($1.30 - 1.95 \text{ grams/m}^2/\text{day}$). There have been no deaths, serious adverse events or severe adverse events reported in subjects who received single doses of RP103, nor in patients receiving 600 mg twice a day for the treatment of Huntington's disease (Raptor Therapeutics Inc. Cysteamine Bitartrate Delayed-release 75 mg capsules, Investigator's Brochure, 1st Edition -January 13, 2012).

6.3 Safety issues related to placebo

Currently, there are no FDA approved therapies for NAFLD. Therefore, use of a placebo is justified for comparison of efficacy with cysteamine DR. There are no known safety issues with the placebo capsules.

6.4 Management of adverse effects attributed to cysteamine bitartrate DR

During the trial, if a participant develops side effects thought to be due to the study medication and of a severity that requires cessation of study medication, the medication will be stopped for 4 weeks. If the side effects disappear, an attempt will be made to reintroduce the study medication after 4 weeks. If the symptoms reappear, study medication will be once again stopped and the patient will no longer receive the study medication, but will continue to be followed in the study according to the protocol, in keeping with the "intention-to-treat" paradigm.

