6.11 Procedures for unmasking treatment assignment

Treatment assignments are double masked throughout the study until all data collection for the CyNCh trial has been completed (i.e., after completion of the 24 week post trial follow-up for all participants). Every effort will be made to maintain the masking throughout the study except in emergencies. The code of specific pharmacological treatment will not be broken without the knowledge of the clinical center's principal investigator and the study leadership.

Unmasking of study medication may occur under the following conditions:

- Severe allergic reaction (Stevens-Johnson Syndrome): Study medication is stopped indefinitely. The patient, primary care provider (PCP), and the investigator may be unmasked.
- **Pregnancy during the study:** Study medication will be stopped indefinitely, and the coded medication may be unmasked. The patient, PCP, and investigator will be notified of the associated risks of teratogenicity.
- **Development of hepatotoxicity:** Hepatotoxicity will be defined as the development of jaundice with a serum direct bilirubin of > 1.0 mg/dL and an increase in the baseline ALT and AST value that is two-fold or > 400 U/L during treatment. Study medication will be discontinued; however, there will be no unmasking until study conclusion.

The Data and Safety Monitoring Board will review all instances of unmasking that occur.

7. Statistical design and analysis

7.1 Primary hypothesis:

Cysteamine bitartrate DR at 9-12 mg/kg orally daily for 52 weeks is better than placebo in improving liver histologic parameters as measured by the NAFLD activity score in children with NAFLD.

Secondary aims:

- To assess safety and tolerability of cysteamine DR during the 52 week treatment period
- To assess the effect of cysteamine DR on:
 - Serum alanine aminotransferase (ALT), serum aspartate aminotransferase (AST) and serum γ -glutamyl transferase (GGT).
 - Liver fat as measured by MRI.
 - Markers of oxidation and anti-oxidant status: malondialdehyde, F2 alpha-isoprostane, total antioxidant capacity
 - o Insulin resistance
 - Anthropometrics
 - o Quality of Life
 - o Liver related symptoms

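### Section 6.4 directs reintroduction of study drug after any resolved drug-attributed side effect, without excepting the skin reactions for which 5.10 and 6.11 rule out a restart

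*Protocol*

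**What the plan says.** Three sections of the protocol bear on what happens to study drug after a serious skin reaction.

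- **Section 6.4**, the section on managing adverse effects attributed to cysteamine, applies to "side effects thought to be due to the study medication and of a severity that requires cessation of study medication". The drug is withheld for 4 weeks. Then: "If the side effects disappear, an attempt will be made to reintroduce the study medication after 4 weeks". The only permanent stop that 6.4 states follows recurrence after reintroduction. It names no excluded event and does not refer to 5.10 or 6.11.
- **Section 5.10**, on concomitant conditions, sets a different rule for "major dermatological reactions such as generalized urticaria, bullous rashes, exfoliative dermatitis, or Stevens-Johnson Syndrome, study drug will be discontinued immediately and not restarted". It is more permissive about local skin reactions: "If the rashes clear, the study drug may be restarted". Where medication has been discontinued, it adds that "the study drug will be unmasked and the participant, investigator, and the primary care provider will be notified in order to prevent future exposures".
- **Section 6.11**, on unmasking, states: "Severe allergic reaction (Stevens-Johnson Syndrome): Study medication is stopped indefinitely".

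**The concern.** Section 6.4 is worded as an instruction, not as an option. Its title makes it the natural place for site staff to look when a child has a reaction they attribute to the drug. The bans on restarting sit elsewhere, under headings about concomitant conditions and unmasking. A site that consulted only 6.4 would try to re-expose a child to a drug suspected of causing, for example, Stevens-Johnson Syndrome, although the protocol elsewhere says that child must not receive it again. What is at stake is the safety of individual participants, not the validity of the efficacy comparison.

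**Working it through.** No arithmetic applies. The check is whether one event can fall under all the rules at once, and whether any condition in 6.4 takes that event out of its scope.

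| Event, thought due to study drug, severe enough to stop it, now resolved | 6.4 | 5.10 | 6.11 |
|---|---|---|---|
| Stevens-Johnson Syndrome | Attempt reintroduction after 4 weeks | No restart | Stopped indefinitely |
| Generalized urticaria, bullous rash, exfoliative dermatitis | Attempt reintroduction after 4 weeks | No restart | Not named |
| Local skin reaction | Attempt reintroduction after 4 weeks | Restart permitted | Not named |

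**Does the severity condition exclude the major reactions?** No. Section 6.4 applies when the effect is severe enough to require stopping the drug. Section 5.10 itself requires an immediate stop for these reactions, so they meet the condition.

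**Does the attribution condition exclude them?** No. Section 6.4 needs the effect to be thought due to study medication. The ban in 5.10 on restarting after major reactions does not depend on attribution, so it also covers those that are attributed to the drug. The two sections overlap on exactly that group.

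**Does the requirement that the effect disappear exclude them?** No. A major skin reaction can resolve. Section 5.10 makes clearing a ground for restarting only in the case of local reactions; for major reactions the ban carries no such condition.

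**Does the text state which section prevails?** No. Section 6.4 contains no exception and no cross-reference, and neither 5.10 nor 6.11 says that it overrides 6.4.

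The first two rows of the table are therefore direct conflicts: 6.4 directs what 5.10 forbids, and for Stevens-Johnson Syndrome 6.11 forbids it as well. The third row is shown for contrast only. It shows that 5.10 separates reactions that allow a restart from those that do not, a distinction missing from 6.4.

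**The case against.** The best case for the protocol is that this is ordinary drafting: a general rule in 6.4 and specific exceptions in 5.10 and 6.11. Section 6.4 names no event, while 5.10 names the reactions and is unconditional. A careful reader would probably let the specific ban govern.

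Several safeguards would also have to fail before a child was re-exposed:

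- Section 5.10 requires unmasking and notification, with the stated aim of preventing further exposure.
- Under 6.10.3, a reaction that meets the serious definition is reported to the Data Coordinating Center within one business day for review by the Safety Officer, and the DSMB reviews each such report. Section 7.6 says it does so as the events occur.
- Section 6.11 has the DSMB review every unmasking.
- Reintroduction under 6.4 comes only after 4 weeks, by which time these steps would normally have begun.

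Most of this stands, and it limits the size of the problem. It does not remove it. The protocol leaves precedence to the reader. The unmasking requirement sits in the same section as the ban, so a site relying on 6.4 alone could miss both, and 6.11 only permits unmasking after a severe allergic reaction. A generalized urticaria that does not meet the serious definition would not trigger expedited reporting, although the ban and the unmasking in 5.10 would still apply.

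A reader might infer that the protocol as a whole intends, or is likely to cause, re-exposure after Stevens-Johnson Syndrome. The documents do not support that. Sections 5.10 and 6.11 both show the opposite intention, and the safeguards make re-exposure unlikely.

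**Conclusion.** The point holds as a minor safety correction. As written, 6.4 gives the wrong instruction for major dermatological reactions that are attributed to study drug and have resolved. It contradicts 5.10 for all of them, and 6.11 for Stevens-Johnson Syndrome. The conclusion rests on the wording alone and assumes only that such a reaction can be thought drug-related and can resolve.

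The size cannot be put as a number of children, because the protocol gives no expected frequency for these reactions. The primary analysis is unaffected: the sample size, significance level, outcome definition and grouping by assigned treatment do not depend on which section a site follows.

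A reader might extend the contradiction to hepatotoxicity, since 6.11 also discontinues drug there. The text does not support that: 6.11 neither forbids nor allows a later restart after hepatotoxicity, so there is no opposing instruction for 6.4 to contradict.

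**What to change.** Add an exception to the reintroduction sentence in 6.4: *except after major dermatological reactions (5.10) and events for which 6.11 stops study medication indefinitely, when study drug is not reintroduced*.

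This puts the ban in the section that staff are most likely to consult and settles precedence. The stop-and-retry rule stays in place for all other side effects. The cost is one clause, with no added visits, tests or patients and no change to the analysis.

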6.5 Safety issues related to MRI

Standard safety precautions: screening; exclusion of potential participants with contraindications to MR. MRI is a minimal risk procedure if standard precautions and practice are exercised. Standard safety issues for MRI procedures include: claustrophobia, anxiety, discomfort from lying supine for 30 minutes, hearing loss, and heating of metal in the body. Patients will be screened by questionnaire and excluded when the presence of metal in the body is known or suspected. Sources include the presence of a cardiac pacemaker or defibrillator; metal fragments in eyes, skin, body; heart valve replacement, brain clips, venous umbrella; being a sheet-metal worker or welder; aneurysm surgery, intracranial bypass, renal, aortic clips; prosthetic devices such as middle ear, eye, joint or penile implants, joint replacements; hearing aid, neurostimulator, insulin pump; intrauterine device; shunts/stents, metal mesh/coil implants; metal plate/pin/screws/wires, or any other metal implants such as permanent eyeliner or eyebrows.

6.6 Safety issues related to end of treatment liver biopsy

Participants will have one liver biopsy done for research purposes after 52 weeks of treatment. About 20% of people who have a liver biopsy have some degree of pain over the liver that may last a few minutes up to several hours. This occasionally requires pain medication and usually disappears completely within a day or two. A rare complication of liver biopsy is severe bleeding such that a blood transfusion or even radiological/surgical interventions are required to stop the bleeding (between 1 in 1,000 and 1 in 5,000). Very rarely (less than 1 in 10,000 cases) death has occurred from bleeding after a biopsy. We intend to minimize the risks associated with liver biopsy (a) by requiring that each of the physicians who will obtain liver biopsies in the NASH CRN be very experienced in safely obtaining the liver biopsy specimens, (b) by not enrolling subjects with clinical cirrhosis or subjects with coagulopathy, and (c) by adhering to good clinical practice in performing the liver biopsy which was well tolerated and there were no serious adverse events⁴⁰.

6.7 Concerns related to participant privacy

It is the investigator's responsibility to conduct the protocol under the current versions of the Declaration of Helsinki, Good Clinical Practice, and rules of local IRBs. The investigator must ensure that the child's and parent's anonymity be maintained in their data submission to the Data Coordinating Center and IRB. Participants will be identified only by an identification code but not by their name, SSN, or hospital medical record number. Investigators will maintain a separate confidential enrollment log which matches identifying codes with the patients' names and addresses (i.e., available only to local clinic staff). All study material will be maintained in strict confidence.

6.8 Concerns related to specimen repository

It is anticipated that serum, plasma, DNA, and liver tissue from the participants will be stored for future studies related to NAFLD and possibly other liver/metabolic diseases. These samples will be stored in the NIDDK Genetics Repository and the NIDDK Biosample Repository. The NASH CRN Steering Committee will follow the NIDDK standards for (a) obtaining a separate informed consent, (b) storage, (c) transportation of the material, (d) who will have access to the material, and (e) the NIDDK and NASH CRN will follow their policies addressing what investigations will be conducted.

6.9 Food and Drug Administration

The CyNCh trial will be conducted under an Investigational New Drug application (IND # 114,924) held by the NIDDK. The investigators will complete a Statement of Investigator (FDA Form 1572) and must obtain IRB approval per the Code of Federal Regulations before the initiation of the CyNCh trial. The trial will not begin until the IND application is in effect. The safety data required to meet IND regulatory requirements will be collected through adverse event reporting by the clinic investigators and will be provided by the Data Coordinating Center to the NIDDK for transmission to the FDA, the Steering Committee, and the DSMB.

6.10 Adverse event reporting

The CyNCh trial investigators and staff will monitor and report adverse events to ensure patient safety. There are two separate sets of government regulations that apply to unanticipated or adverse events in research studies: (1) 45 CFR Part 46, Subpart A; the "Common Rule"⁷⁹, shared by 17 Departments and Agencies and (2) 21 CFR 312⁸⁰, the FDA regulation for adverse events. The Common Rule requires written procedures and policies for ensuring reporting of "unanticipated problems" involving risks to participants to IRBs, appropriate institutional officials, and the Department or Agency Head. The FDA regulation (21 CFR 312.66) requires reporting of "unanticipated problems" involving risks to participants to participants to IRBs and notification of the FDA and participating investigators of any adverse event associated with the use of a test article that is "both serious and unexpected." Since the definitions and reporting requirements for unanticipated events differ between the two sets of Federal regulations, the CyNCh trial definitions and procedures for adverse events are designed to satisfy both sets of requirements.

